## 7.1.3 Other study parameters (if applicable)

NA

## 7.2 Randomisation, blinding and treatment allocation

Patients will be randomized using a central web-based and validated computer program (ALEA) made available by the Clinical Research Unit(CRU) in the AMC. Randomisation will be stratified by type of psychogenic jerks (in extremity vs. abdominal jerks), using variable permuted blocks.

Randomisation lists will be handed by the CRU to the AMC pharmacy, who will safeguard the code. If needed, the randomization code can be broken by the pharmacy. Neither the subject, nor the investigator is informed about allocated therapy. Serious adverse events like life-threatening side-effects, will be an indication for breaking the code for that specific subject. Non-serious adverse events will be treated, but will not be an indication for breaking the randomization code

## 7.3 Study procedures

## 7.3.1 Neurological examination

During the study, patients will undergo systematic neurological examinations that will be videotaped. The neurological examination will take approximately half an hour. During the study, weakness will be examined using the Medical Research Counsil(MRC)-scale. Psychiatric testing and evaluation of disability

- Patients will be asked to fill in some questionnaires concerning specific psychiatric conditions (mood disorders, anxiety and obsessive compulsive behaviour) and on the severity of disability during their visits. This will take approximately an hour per visit.
- Patients will participate in a psychiatric interview, the MINI-Plus, during their visits. On the first visit this interview will focus on current and previous DSM-IV diagnoses, while in the later visits only current diagnoses will be evaluated. During the first visit this will take approximately 1½ hour, in the later visits this will take approximately half an hour.
- The psychiatric interviews will be videotaped to be able to evaluate certain jerk characteristics for a longer period.

## 7.3.2 Interview

During their visits, patients will be interviewed by an independent investigator who will inquire about the effect of the treatment and whether patients would want to continue it considering all advantages and disadvantages. Furthermore the patients CGI-S and CGI-I will be evaluated. Patients will be asked if they think they were treated with BoNT or placebo during the trial phase of the study. Finally, the occurrence of adverse effects will be assessed. The entire interview will take approximately half an hour.

# 7.3.3 Duration of the visits

In total, the first visit will take approximately 5 hours, including the injection of BoNT or placebo. The following visits including assessments will take approximately 3 hours.

# 7.3.4 Scheme of the different assessments per visit

See also the time schedule of the study on page 17

# Baseline (T = 0):

- Neurological examination, recorded on video
- Psychiatric interview, recorded on video
- Questionnaires (psychiatry, disability and tic assessment)
- CGI severity by examiner (based on video) and patient
- Counting of the amount of jerks during 10 minutes of the psychiatric interview on video
- UMRS and PMD scale scores based on the recorded video during neurological examination
- fMRI scan (when participating in this sub-study)

## T= 16 weeks:

- Neurological examination, recorded on video
- Psychiatric interview, recorded on video
- Questionnaires (psychiatry, disability and tic assessment)
- CGI severity by examiner based on video neurological examination
- CGI-improvement relative to T = 0 by examiner based on video neurological examination
- Counting the amount of jerks during 10 minutes of the psychiatric interview on video
- UMRS and PMD scores based on the recorded video during neurological examination
- Interview (treatment effective, placebo or BoNT, CGI-S, CGI-I, VAS, adverse events)
- MRC weakness
- fMRI scan (when participating in this sub-study)

## T = 16 months

- Neurological examination, recorded on video
- Psychiatric interview, recorded on video
- Questionnaires (psychiatry, disability and jerk assessment)
- CGI severity by examiner based on video neurological examination
- CGI-improvement relative to T=0 and T=16 by examiner based on video neurological examination
- Counting the amount of jerks during 10 minutes of the psychiatric interview on video
- UMRS and PMD scale scores based on the recorded video during neurological examination
- Interview (treatment effective, CGI-S, CGI-I, adverse events)
- MRC weakness

# 7.4 Withdrawal of individual subjects

Subjects can leave the study at any time for any reason if they wish to do so without any consequences. The investigator can decide to withdraw a subject from the study for urgent medical reasons.

# 7.4.1 Specific criteria for withdrawal

NA

# 7.5 Replacement of individual subjects after withdrawal

Subjects will not be replaced after withdrawal.

# 7.6 Follow-up of subjects withdrawn from treatment

When patients withdraw from the study they will be asked to come to the Academic Medical Center one last time for neurological and psychiatric evaluation. Reason of withdrawal, if given, will be evaluated. These data will be used to evaluate the endpoints. If they refuse to come, their last observation is carried forward in the statistical analyses.

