## 1. INTRODUCTION AND RATIONALE

Botulinum neurotoxin (BoNT) has emerged as a useful therapy for several movement disorders associated with muscle overactivity. When BoNT is injected in the muscles, the toxin produces local chemodenervation by blocking the release of acetelylcholine at the neuromuscular junctions. It thereby renders the muscle (partially) unable to contract for a period of 3 to 4 months. The most common side effects of BoNT are local weakness and pain. These side effects are reversible as well.

BoNT is an effective treatment for several disorders, for example for cervical dystonia and blepharospasm, diseases for which therapeutic options previously were restricted.
Botulinum toxin seems a promising therapy for other movement disorders associated with muscle overactivity as well, including jerky movement disorders. We hypothesize that BoNT is an effective treatment for jerky movement disorders of psychogenic origin.

Psychogenic movement disorders are disorders that cannot be accounted for by any known neurologic ("organic") syndrome and encompass a diversity of hyperkinetic movements. Psychogenic movement disorders are amongst the commonest of unexplained neurological symptoms and are supposed to exist in at least 2–9% of patients seen in movement disorder clinics. Of patients with psychogenic movement disorders, 22% were shown to have psychogenic jerks (myoclonus and tics). Although there are some general features common to all functional movement disorders, diagnosis may be difficult. Diagnosis of functional jerks however is largely assisted by the results of EMG and EEG. When the EEG consistently shows a characteristic pre-movement potential (Bereitschaftspotential), the diagnosis psychogenic jerks can be made quite certain.

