## 7. METHODS

## 7.1 Study parameters/endpoints

## 7.1.1 Main study parameter/endpoint

The primary study endpoint for the trial will be improvement of motor characteristics of the jerk of interest assessed with the Clinical Global Impression - Improvement scale (CGI-I). On this 7 point scale can be assessed how much the patients illness has improved or worsened relative to the baseline state. It can be rated as: 1, very much improved; 2, much improved; 3, minimally improved; 4, no change; 5, minimally worse; 6, much worse; or 7, very much worse. We will consider a score 1, 2 or 3 determined by an experienced researcher as reaching the primary outcome. The primary outcome will be determined 4 weeks after the second injection (t=16 weeks) as the optimal effect of BoNT is between 4 and 8 weeks after the injection. One researcher who is blind to allocated treatment will assess the CGI-I in all patients based on videos of the patient.

The CGI-I scale is one of the few rating scales that is considered suitable for psychogenic movement disorders at this moment.

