## 9.2 Univariate analysis

An intention to treat analysis will be performed with regard to the trial results. The difference in the proportions of patients reaching the primary outcome measure between the groups treated with BoNT and with placebo will be assessed using the  $\chi 2$  statistic or Fisher's exact test, when appropriate. For the secondary outcome measures, proportional differences between the groups will be tested with the  $\chi 2$  statistic. Difference in continuous secondary outcome measures will be assessed with the Students t-test or ANCOVA. For the long term effects, the assessments of individual patients at t=16 months will be compared with previous assessments using tests for paired data (paired t-test, McNemar's symmetry  $\chi 2$  test for paired responses) or the mean difference between T = 16 months and T = 0. Finally, we will analyse repeated measures data using mixed effects models. In all analyses statistical uncertainties will be expressed in 95% confidence intervals.

Concerning the fMRI study the main study outcome measure is the difference in BOLD signal between scans of patients with psychogenic jerks before and after treatment with BoNT. Secondary outcome will be patterns of representations of external space and body scheme in patients compared to the patterns seen in healthy subjects. Another secondary outcome will be the performance of patients in the self-referenced and target-based finger movement task itself.

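### Section 7.6 lets a rating from an undated exit visit stand in for the week-16 primary CGI-I, and no section asks patients who stop treatment early to attend at week 16

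*Protocol*

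**What the plan says.** Four parts of the protocol bear on this.

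- **Section 7.6** is headed as follow-up of subjects withdrawn from treatment, but its text opens "When patients withdraw from the study". It says "they will be asked to come to the Academic Medical Center one last time for neurological and psychiatric evaluation", and then "These data will be used to evaluate the endpoints". For those who decline that visit, "If they refuse to come, their last observation is carried forward in the statistical analyses". It gives no week or window for the visit.
- **Section 7.1.1** fixes the time of the primary endpoint: "The primary outcome will be determined 4 weeks after the second injection (t=16 weeks"). The reason given is pharmacological: "as the optimal effect of BoNT is between 4 and 8 weeks after the injection".
- **Section 1** says of an injected muscle: "It thereby renders the muscle (partially) unable to contract for a period of 3 to 4 months".
- **Section 9.2** states that "An intention to treat analysis will be performed with regard to the trial results".

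The Assessments part of section 3 schedules ratings at baseline, 16 weeks and 16 months only. Section 4.4 expects practically no withdrawals in the trial phase and allows for 10%.

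**The concern.** The protocol's own reason for choosing week 16 is that a rating depends on how long ago the muscle was injected. Section 7.6 then admits ratings taken at any time since injection. A patient who leaves before week 16 and attends the exit visit gets a CGI-I that section 7.6 uses for the endpoints, with nothing to mark it as off-schedule. No rating is scheduled between baseline and week 16, so for such a patient it is the only post-baseline rating there is.

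Section 7.6 also does not separate stopping injections from leaving the study. A patient who stops treatment early but is willing to return could still supply a true week-16 rating, and no section says to ask for it.

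What is at stake is whether the primary comparison describes week-16 status in everyone randomised, as an intention-to-treat analysis at that time requires. This is a matter of data collection: a later analysis plan cannot recover a week-16 video that was never recorded. The point concerns patients who attend the exit visit, not the carry-forward rule for those who refuse it.

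**Working it through.** **1. The protocol's figure.** Inputs from section 4.4: 0.30 vs 0.70, two-sided 0.05, chi-square, 80% power. The pooled-variance formula without continuity correction gives 24 per arm, as stated, with approximate power of 81.2%. Inflation for withdrawal is 24 / 0.90 = 26.7, so 27 per arm. Exact enumeration of the uncorrected chi-square test with 27 per arm gives power of 84.0% (the normal approximation gives 85.7%). The exact figure is the reference below.

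**2. Timing on the protocol's statements.** Injection 1 is at week 0, injection 2 about 3 months later, and the primary rating at week 16. Peak effect is 4 to 8 weeks after an injection, and the effect lasts 3 to 4 months.

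| Rating taken | Position in the cycle |
|---|---|
| Week 16, as planned | 4 weeks after injection 2, start of the stated peak |
| Exit visit at week 5 | within the stated peak of injection 1 |
| Exit visit at about week 12, no injection 2 | past the stated peak of injection 1 |
| Week 16, no injection 2 | towards the end of the stated 3 to 4 months |

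A week-5 exit rating can look better than the same patient's week-16 status. A week-12 exit rating may be better or worse than it.

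**3. Number affected.** 10% of 27 = 2.7 per arm, about 5 of 54. One patient is worth 1/27 = 3.7 percentage points in an arm.

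**4. Size, as assumed scenarios.** The documents give no response rates for exit-visit ratings, so these are bounds and not forecasts. Would-be responders among withdrawals: BoNT 0.70 × 2.7 = 1.89; placebo 0.30 × 2.7 = 0.81. If all are rated non-responders:

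- BoNT rate = 0.70 − 1.89/27 = 0.63
- placebo rate = 0.30 − 0.81/27 = 0.27

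The half rows halve each loss. In the last row the would-be BoNT non-responders (0.30 × 2.7 = 0.81) are all rated responders: 0.70 + 0.81/27 = 0.73.

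| Scenario (27 per arm) | Placebo | BoNT | Difference | Exact power |
|---|---|---|---|---|
| No misclassification | 30% | 70% | 40 points | 84% |
| Half of would-be responders lost, BoNT only | 30% | 66.5% | 36.5 points | 76% |
| Half lost, both arms | 28.5% | 66.5% | 38 points | 80% |
| All lost, BoNT only | 30% | 63% | 33 points | 67% |
| All lost, both arms | 27% | 63% | 36 points | 76% |
| BoNT non-responders all rated responders | 30% | 73% | 43 points | 89% |

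The rise in the last row is not a gain, because the extra difference is spurious.

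**5. On a realised result.** Take 8/27 vs 19/27 responders, close to the design rates: chi-square p = 0.0028. With three BoNT responders re-rated as non-responders (8 vs 16), p = 0.0285. With four (8 vs 15), p = 0.054. The planned withdrawal allowance does not overturn a result at the design effect, but one patient can decide a result near the boundary.

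**The case against.** The strongest reply is that section 7.6 applies to patients who leave the study, not to those who merely decline an injection. Section 7.1.1 has one blinded researcher rate all patients, section 7.3.4 schedules the week-16 visit, and section 9.2 promises intention to treat. Read together, a patient who skips the second injection but stays in the study would be rated at week 16. For a patient who really leaves at week 5, no injection is due then to decline, and an exit visit may be the only rating obtainable. The protocol also expects practically no withdrawals.

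Much of this stands, and it rules out several stronger statements that a reader might infer:

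- *That the visit takes place when injections stop, or that such patients are never asked back.* The text says neither. It names no week, and it starts from withdrawal from the study. What can be said is that the visit is undated, that heading and text disagree on whom they cover, and that no section states that patients who stop treatment early are still asked to week 16.
- *That the error cannot cancel because saline has no time course.* Section 4.4 says the placebo effect may be large, and the protocol does not say how it changes over time. A stable placebo response would be an assumption.
- *That power falls to 59%.* That figure (30% vs 60%) needs all 2.7 BoNT withdrawals to be would-be responders rated as non-responders, with no change on placebo. At the design rate only about 1.9 of them would be responders.

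The reply does not remove the core. Section 7.6 is a stated rule, not a gap left for an analysis plan: exit-visit data are used for the endpoints, with no limit on when they were collected.

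**Conclusion.** The point holds, and the protocol should be changed. Section 7.6 allows off-schedule ratings into a primary endpoint that section 7.1.1 ties to a set time after the second injection, and it does not separate stopping treatment from leaving the study.

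The direction of bias is not known: an exit near peak effect could inflate the difference, and one past the peak could dilute it. The size is modest. About 2.7 patients per arm are affected at the 10% allowance, and fewer if withdrawals are as rare as section 4.4 expects. The assumed worst case for power at the design response rates is a fall from 84% to 67% with only the BoNT arm affected, or to 76% with both arms affected. These figures rest on complete misclassification of would-be responders, for which the documents give no data. They show what the rule permits, not what is likely.

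**What to change.** In section 7.6:

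1. Separate stopping injections from withdrawing consent, and make heading and text cover the same patients.
2. Ask every randomised patient who has not withdrawn consent to attend the scheduled week-16 visit. Use that rating as the primary outcome whatever injections were received.
3. Offer an early exit assessment only to those who will not attend at week 16, and record its date.
4. For those patients, treat the week-16 outcome as missing under one rule stated in advance for the primary analysis, for example non-responder in both arms. Use the exit rating in a sensitivity analysis.

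The cost is one protocol paragraph and no new visit type, for about five or six patients at most. Sample size, doses and treatment rules do not change. There are two downsides. A few patients who would have come at once may not return at week 16. And a non-responder rule has its own price: if none of the 10% attended, the rates would be 27% vs 63% and exact power 76%, as in the both-arms row above. Each patient who does attend reduces that loss, and the rule is the same in both arms and does not depend on when the patient left.

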#### Intervention

BoNT or placebo (0.9% sterile saline) will be injected in muscles involved in the jerky movement. In appearance the placebo is indistinguishable from BoNT. The muscles that will be injected will be determined by a neurophysiologist experienced in treatment with BoNT according to the pattern of movements visible and according to the involved muscles measured with EMG. The number of muscles injected may differ per patient. The neurophysiologist will determine the doses to be administered. These will be similar to those used for involvement of the same muscle by other movement disorders (typically dystonia). Placebo injections consist of an equivalent volume of 0.9% sterile saline. All injections will be given by an experienced neurophysiologist, who will remain blind to the treatment allocation and will not be involved in the outcome assessments.

As dose response differs individually, patients will be treated two times. The first treatment will take place after the baseline assessment. The second treatment will take place 3 months hereafter; this is the usual time interval in the treatment of dystonia. To optimize therapy, the dose and if necessary the injection sites may be adjusted in the second session according to degree of response and occurrence of muscle weakness. After 16 weeks, the trial period ends (see also time scheme, page 14).

[figure not shown]
After the trial period, all patients will be assigned to treatment with BoNT to establish the long-term effects. In this phase of the study, patients will receive a total of 4 times injections with BoNT at 3 month intervals. This results in a follow-up period of 12 months for all patients included in the study. The length of this follow up is considered necessary because of

several reasons. First and most important, an effect of therapy may diminish over time in these patients with a chronic disorder with frequently co-occurring disease. Second, it is considered an evaluation period for certain secondary study objectives, as it may take longer than the trial period before an effect on for example, concurrent psychiatric disease is observed. Finally, this way it is possible to evaluate whether optimalization of treatment results in better response to therapy in these patients.

Additionally in 16 of 54 patients an fMRI scan will be performed before and at the end of the trial (16 weeks).

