## **Assessments**

Patients will be assessed at baseline, 16 weeks (the trial period) and after 16 months (follow-up study). Information on improvement, severity and frequency of jerks, the effect of therapy, disability and psychiatric disorders will be acquired with an interview and with questionnaires. Furthermore patients will be neurologically examined and recorded on video. A small part of the patients (n=16) will undergo an fMRI scan before and after treatment.

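### The carry-forward rule in Section 7.6 yields no primary CGI-I value for a patient who leaves before week 16 and refuses the exit visit, and at 16 months it can enter a placebo-period value as a long-term BoNT outcome

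*Protocol*

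**What the plan says.** Section 7.6 has two steps for a patient who withdraws. First, "they will be asked to come to the Academic Medical Center one last time for neurological and psychiatric evaluation", and those data serve the endpoints. Second, "If they refuse to come, their last observation is carried forward in the statistical analyses". The second step is not limited to particular outcomes or to one phase of the study.

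The assessment schedule is in Section 3: "Patients will be assessed at baseline, 16 weeks (the trial period) and after 16 months (follow-up study"). The visit lists in Section 7.3.4 agree with it.

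Section 7.1.1 describes the primary scale as showing "how much the patients illness has improved or worsened relative to the baseline state". It fixes the time: "The primary outcome will be determined 4 weeks after the second injection (t=16 weeks"). It also defines response: "We will consider a score 1, 2 or 3 determined by an experienced researcher as reaching the primary outcome". At baseline the only CGI item listed is "CGI severity by examiner (based on video) and patient". The examiner's improvement rating first appears in the week-16 list.

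Section 9.2 plans an intention-to-treat analysis of the trial results and paired tests for the long-term effects. Section 7.1.2 compares the 16-month assessments with both baseline and week 16. Between those two times treatment changes for half the patients: "After the trial period, all patients will be assigned to treatment with BoNT to establish the long-term effects".

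**The concern.** Carry-forward needs an earlier value of the same variable. For CGI-I there is none before week 16, so the stated rule cannot be carried out on the primary endpoint for the one group it is meant to cover. Intention to treat keeps such a patient in the analysis, but nothing says whether that patient counts as improved, as not improved, or drops out of the denominator. The choice would then be made after the data are seen.

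At 16 months the rule can be carried out, but it gives the wrong quantity for some patients. The week-16 value of a former placebo patient was obtained on placebo. Carried to month 16, it is counted as an outcome of a year of BoNT. For any carried patient, the paired comparison of month 16 with week 16 receives a difference of zero that nobody observed.

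**Working it through.** **Inputs.** From Section 4.4: two-sided 5% chi-square test, 80% power, response 0.30 on placebo and 0.70 on BoNT, 24 evaluable per group, 10% withdrawal, 27 per arm, 54 in total. From Sections 3, 7.1.1 and 7.3.4: the written visit schedule and the CGI items at each visit. The responder counts and follow-up losses below are assumptions for illustration.

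**1. The plan's own sample size.** n = [1.960·√(2·0.5·0.5) + 0.842·√(0.30·0.70 + 0.70·0.30)]² / 0.40² = [1.386 + 0.546]² / 0.16 = 23.3, so 24 per group. Then 24/0.90 = 26.7, so 27 per arm. Both figures reproduce. Power at 24 per group is 81.2%.

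**2. Which CGI-I values could be carried?**
- Baseline: severity only, so none.
- Second injection session at 3 months: the dose may be adjusted to the response, but no CGI-I is listed, and the injector takes no part in outcome assessment.
- Week 16: first CGI-I.

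A patient who leaves before week 16 and refuses the exit visit has no CGI-I to carry.

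**3. How many patients?** 10% of 27 is 2.7, so at most about 3 per arm; 10% of 54 is 5.4, so 5 to 6 in all. This is a ceiling: it requires every withdrawal to fall before week 16 and every such patient to refuse the visit.

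**4. Does the handling matter?** Take 24 observed and 3 missing per arm. Pearson chi-square without continuity correction, z = (p₁ − p₂)/√(2·p̄·(1 − p̄)/n):

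| Observed (BoNT vs placebo) | Handling of the missing | Compared | p |
|---|---|---|---|
| 14/24 vs 7/24 | available cases | 14/24 vs 7/24 | 0.042 |
| | not improved, both arms | 14/27 vs 7/27 | 0.051 |
| | best case for BoNT | 17/27 vs 7/27 | 0.006 |
| | worst case for BoNT | 14/27 vs 10/27 | 0.27 |
| 17/24 vs 7/24 | available cases | 17/24 vs 7/24 | 0.004 |
| | not improved, both arms | 17/27 vs 7/27 | 0.006 |
| | best case for BoNT | 20/27 vs 7/27 | 0.0004 |
| | worst case for BoNT | 17/27 vs 10/27 | 0.057 |

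The second block is about the planned effect (0.70·24 = 16.8 and 0.30·24 = 7.2). With only one refuser per arm at planned rates, 18/26 vs 8/26, the worst case is 18/27 vs 9/27: z = 0.333/0.136 = 2.45, p = 0.014.

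**5. Month 16.** Let a share w of former placebo patients be carried, with response 0.30 on placebo and 0.70 on BoNT. The apparent 16-month rate in that group is (1 − w)·0.70 + w·0.30, which is 0.66, 0.62 and 0.58 for w = 10%, 20% and 30%, instead of 0.70. For any score measured at both times, the carried difference is exactly 0. If patients who leave resemble those who stay, the mean week-16 to month-16 change is therefore multiplied by (1 − w). The separate 16-month CGI-I rated against week 16 again has no earlier value to carry.

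**6. Cost of counting the missing as not improved.** If 10% are missing regardless of response, the rates become 0.9·0.30 = 0.27 and 0.9·0.70 = 0.63. Power at 27 per arm = Φ{[0.36 − 1.960·√(2·0.45·0.55/27)] / √[(0.27·0.73 + 0.63·0.37)/27]} = Φ{(0.360 − 0.265)/0.126} = Φ(0.75), about 77%. With complete data at 27 per arm it is 85.7%.

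**The case against.** The strongest reply is that few patients will be exposed. Section 7.6 seeks an exit visit first, and a patient who attends can be rated, though not necessarily four weeks after the second injection. Section 4.4 expects almost no withdrawals in the trial phase and treats 10% as a margin. The nearest analogue of carry-forward, no change since baseline, is a CGI-I of 4 and hence non-response, which is also the remedy proposed here. All of this limits the size of the problem. It does not make the rule executable, because the document never states that analogue, and it is not a carried observation.

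A reader might infer four stronger conclusions that the documents do not support.

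- That 5 to 6 patients will be affected. That figure is a maximum.
- That the primary result hangs on this rule. At about the planned effect the two ordinary conventions agree (p=0.004 and 0.006). The p=0.057 requires every missing placebo patient to be scored improved and every missing BoNT patient not improved, which is a bound and not a plausible reading of Section 7.6. The crossing from 0.042 to 0.051 uses counts chosen below the planned effect (29 percentage points observed against 40 planned).
- That carry-forward contradicts the mixed effects models in Section 9.2. Those models stand beside t-tests, ANCOVA and paired tests; imputing for some analyses and modelling observed data in another is compatible.
- That the 16-month values inflate the benefit of BoNT. Under the planned rates they lower the apparent response in former placebo patients, and the zeros pull the change from week 16 towards nothing.

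The 16-month part is also secondary: the follow-up is uncontrolled and was not powered. For scales rated at baseline, carrying that value to week 16 can be done; preferring another method there is a matter of choice and is not pressed here.

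**Conclusion.** The point holds in limited form. Section 7.6 states a missing-data rule that cannot be applied to the primary endpoint for a patient who leaves before week 16 and refuses the exit visit. It therefore leaves the intention-to-treat responder analysis undefined for that patient. This is a stated rule that fails, not a detail deferred to an analysis plan.

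The exposure in the trial phase is at most about 3 of 27 per arm, assuming the full 10% withdraw early and all refuse. That is enough to move a borderline result across 5% between two ordinary conventions, but not a result near the planned effect.

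At 16 months the same rule mixes placebo-period values into BoNT outcomes for former placebo patients who leave follow-up and refuse the visit, and it forces a zero change from week 16 for every carried patient. The size depends on a follow-up withdrawal rate that the document does not give; the 10% to 30% range is an assumption.

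This should be fixed before unblinding. It does not put the trial's validity in doubt.

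**What to change.** Amend Section 7.6, and Section 9.2 to match:

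- Primary endpoint: drop carry-forward. Patients without a CGI-I rating count as not improved in both arms, with a best/worst-case analysis reported as a bound.
- Data collection: ask patients who stop injections to be videoed at week 16 all the same, if they agree, so that fewer ratings are missing.
- Follow-up: never carry a value across the week-16 switch to BoNT. Report observed 16-month data with the number of patients assessed as the denominator.

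The cost is protocol wording and some extra effort to obtain week-16 videos. Counting missing patients as not improved dilutes the effect slightly: about 77% power at 27 per arm if the full 10% are missing, against 81% for the plan's 24 evaluable per group. The loss is smaller if withdrawals are as rare as Section 4.4 expects.
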